9.3 Recording and reporting of SAEs, AESIs, SARs AND SUSARs

All **SAEs** / **SUSARs** occurring from the **point of randomisation** until the final trial visit following follow-up (or 100 days post cessation of trial treatment (if discontinued early), must be recorded on the SAE Form and sent to the Sponsor and the Leicester Clinical Trials Unit (LCTU) **within 24 hours** of the research staff becoming aware of the event.

Page 28 of 60

After informed consent has been obtained but prior to initiation of study drug, only serious adverse events caused by a protocol-mandated intervention (e.g., invasive procedures such as biopsies, discontinuation of medications) should be reported.

Accidental overdoses or medication errors must report to the Sponsor within 24 hours after learning of the event, regardless of relationship to study drug.

Adverse events of special interest (AESIs) are required to be reported by the investigator to the Sponsor immediately (i.e., no more than 24 hours after learning of the event.

Once all resulting queries have been resolved, the Sponsor will send an acknowledgement of the closure of the SAE, all correspondence and signed SAE forms will be retained by the site, within the Trial Master File and electronically on the Sponsor SAE database.

For each **SAEs / SUSARs** the following information will be collected:

- full details in medical terms and case description
- event duration (start and end dates, if applicable)
- action taken
- outcome
- seriousness criteria
- causality (i.e. relatedness to trial drug / investigation), in the opinion of the investigator
- whether the event would be considered anticipated.

Any change of condition or other follow-up information should be faxed to the Sponsor as soon as it is available or at least within 24 hours of the information becoming available. Events will be followed up until the event has resolved or a final outcome has been reached.

All SAEs assigned by the CI or delegate (or following central review) as both suspected to be related to IMP-treatment and unexpected will be classified as SUSARs and will be subject to expedited reporting to the Medicines and Healthcare Products Regulatory Agency (MHRA). The sponsor will inform the MHRA and the REC of SUSARs within the required expedited reporting timescales. Fatal or life-threatening SUSARs must be reported within 7 days and all other SUSARs within 15 days.

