3.5.2 Secondary outcomes (**indicates this data is held on Macro database*)

1. Safety and tolerability

- AE event rate in the 48 weeks of the trial from first dose*
- SAE event rate in the 48 weeks of the trial from first dose*

2. Patient related outcomes (PROs) (weeks 0, 4, 12, 24, 36 and 48)*

- St George's Respiratory Questionnaire for COPD patients (SGRQ-c)
 Total
- COPD Assessment Test (CAT)
- mMRC Dyspnoea Scale
- Visual analogue score (VAS)
 - Dyspnoea
 - Cough
 - Sputum production
- Sputum purulence colour card

3. Lung function (Weeks 0 and 48)

- Pre and post BD spirometry*
 - FEV1
 - FEV1 % predicted
 - FVC
 - FEV1/FVC %
 - BD reversibility %
- Whole body plethysmography (body box)*
 - TLC
 - RV
 - RV/TLC %

4. Inflammation (Weeks 0, 4, 12, 24, 36)

- Cell count
 - Blood inflammatory cell differentials*
 - o WBC
 - \circ Eosinophils
 - \circ Neutrophils
 - Sputum inflammatory cell differentials
 - Eosinophils
 - o Neutrophils
 - o Macrophages
 - \circ Lymphocytes
 - Epithelial cells
 - o Total

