4 TRIAL DESIGN

This is a single-centre, double-blind, placebo- controlled, parallel group, randomised controlled trial to assess the efficacy and safety of anti-ST2 compared to placebo, in patients with moderate to very severe COPD (GOLD II-IV). Anti-ST2 will be administered via subcutaneous injection once every 4 weeks (Week 0, 4, 8, 12, 16, 20, 24, 28, 32, 36, 40, and 44) during the 48-week treatment period. The treatment period will be followed by a 12-week follow-up period (i.e washout period). An overview of the trial design is presented in Figure 1.

After signing the informed consent at the initial visit, patients will enter a screening period within 7-14 days of randomisation. Patients who qualify to participate in the trial will be randomised into a 48-week treatment period in which they will receive either 490 mg anti-ST2 or a matching placebo. Patients will be evaluated for an additional 12 weeks following completion of the efficacy endpoint (visit 13, week 48). Treatment groups will remain blinded until the 60-week follow-up period is completed, and trial database is locked. Visit procedures will be performed as shown in Appendix 1.

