7.10 Withdrawal criteria

The only specified withdrawal criteria for this study will be for participants that miss more than one dose of the study treatment, or who delay a scheduled study visit for >4 weeks. These participants will remain in follow-up for the trial duration. If a participant wishes to completely withdraw from the study, or is withdrawn for reasons other than a missed or delayed dose, the research team will encourage them to undertake the 'withdrawal visit' procedures and assessments which will signify the end of their participation. This will include participants who withdraw via telephone. It will be at the participant's discretion whether or not they attend the withdrawal visit. Withdrawal visits should be completed as soon as possible, however the timeframe will be largely dependent on what the participants finds acceptable.

Every effort should be made by the research team to keep the participants in the trial. However, participants have the right to withdraw their consent to take part in the trial at any time without having to give a reason and this will not affect their future care. Withdrawal details and reasons (if known) should be recorded on the withdrawal/loss to follow up CRF and in the medical notes. In addition, the investigator may discontinue a participant from the trial at any time if the investigator considers it necessary. The IMP will also be discontinued in the case of an adverse event which the investigator considers sufficient to jeopardise the safety of the trial participant. Participants who want to discontinue protocolled treatment should be encouraged to remain in the trial and continue to be followed-up as per protocol or as of routine care.

Every effort should be made to keep the participant in the trial to collect important efficacy and safety data. Withdrawals from the trial should be discussed with the CI or their deputy and the Trial Manager. If a participant has withdrawn from the trial for any reason, then his/her screening and participant ID number(s) cannot be issued to another participant.

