8.7 Dosage modifications

There will not be any dose modification during the trial (see Section 8.10 for non IMP medication changes).

If a participant has an anaphylactic reaction to the drug or placebo, they will discontinue from protocolled treatment but remain in follow-up. If the drug was stopped due to a clinical reason such as allergic reaction, we will err on side of caution and not restart the drug in the same participant.

No information on overdose, maximum-tolerated dose, or dose-limiting toxicities has been established at this time.

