9.2 Safety Assessments

All Adverse events (AEs) will be recorded throughout the study whether serious or not. Members of the research team will ask the participants about AEs at each study time point (see Appendix 1) and will complete the participant AE form, which will be a continuous log so as to capture end dates, and the study serious adverse event (SAE) log. This will be evaluated and classed according to the definitions in sections 9.1.

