9.8 Urgent safety measures

The Sponsor and Investigator may take appropriate urgent safety measures to protect clinical trial participants from any immediate hazard to their health and safety. The measures must be taken immediately; Sponsor, MHRA, REC, HRA and R&D approval is not required before implementation.

Reporting of Urgent Safety Measures should adhere to Sponsor SOPs. Sponsor and the regulatory authorities, Genentech and the LCTU must be informed in writing of the measures taken and the circumstances giving rise to those measures, in the form of a substantial amendment within three days. The process for submitting amendments as a result of Urgent Safety Measures is covered in the Sponsor SOPs.

9.9 The type and duration of the follow-up of participants after adverse reactions.

Following an adverse drug reaction (ADR) the participants will be followed-up for an appropriate length of time as dictated by the nature of ADR and their clinical needs. ADR will continue to be recorded and reported for up to 3 months after the last dose of IMP has been administered. Any SUSAR will need to be reported to the Sponsor irrespective of how long after IMP administration the reaction has occurred until resolved.

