# 7 Safety and Adverse Events

All safety data will be presented according to the safety population. Any adverse events and serious adverse events occurring from the first dose throughout the trial period will be recorded on the AE CRF, Sponsor's SAE form and SAE tracking log.

An Adverse Event (AE) is any untoward medical occurrence in a patient, associated with the use of a medicinal product, whether or not considered related to the medicinal product.

Events meeting the definition of an AE include:

- Exacerbation of a chronic condition (except COPD)
- New conditions detected or diagnosed after trial treatment administration even though it may have been present prior to the start of the trial
- Signs, symptoms, or the clinical sequelae of a suspected interaction
- Signs, symptoms, or the clinical sequelae of a suspected overdose of trial treatment
- Any unfavourable and unintended sign (including an abnormal laboratory finding), symptom, or disease temporally associated with the use of a medicinal product, whether or not considered related to the medicinal product
- Recurrence of an intermittent medical condition (e.g., headache) not present at baseline
- Any deterioration in a laboratory value or other clinical test (e.g., ECG, X ray) that is associated with symptoms or leads to a change in study treatment or concomitant treatment or discontinuation from study drug
- Adverse events that are related to a protocol mandated intervention, including those that occur prior to assignment of study treatment (e.g., screening invasive procedures such as biopsies)

Events that **do not** meet the definition of an AE include:

- Medical or surgical procedure (e.g., endoscopy, appendectomy); the condition that leads to the procedure is an AE
- Situations where an untoward medical occurrence did not occur (social admission to a hospital)
- COPD exacerbation, progression, signs and symptoms (unless they are considered to be related to the trial drug by the investigator; then they would constitute a reaction)

An adverse reaction (AR) is an untoward and unintended response(s) related to the study treatment. All cases judged by either the reporting medically qualified professional or the sponsor as having a reasonable suspected causal relationship to the study treatment qualify as adverse reactions.

A Serious Adverse Event (SAE) or Serious Adverse Reaction (SAR) is defined as any adverse event or adverse reaction in a trial participant that:

- Results in death

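### Protocol 9.3 conflicts with Protocol 9.2, the visit schedule and SAP 7 on how long SAEs are recorded for participants who stop dosing but stay in follow-up

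*Protocol*

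**What the plan says.** **The limit.** Protocol 9.3 requires SAEs and SUSARs from randomisation onward to go on the SAE form and be sent within 24 hours, "until the final trial visit following follow-up (or 100 days post cessation of trial treatment (if discontinued early". Neither document defines early discontinuation.

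**Who stays in follow-up.** For participants who miss more than one dose or delay a visit by more than 4 weeks, Protocol 7.10 says: "These participants will remain in follow-up for the trial duration". For anaphylaxis, Protocol 8.7 says "they will discontinue from protocolled treatment but remain in follow-up". Section 7.10 also counts a participant as a completer if they take part to Visit 13, on or off treatment. Protocol 8.10, however, says that participants delayed more than 4 weeks are withdrawn.

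**Recording without that limit.** Protocol 9.2 says AEs "will be recorded throughout the study whether serious or not". SAP 7 says AEs and SAEs "occurring from the first dose throughout the trial period will be recorded", and it names the Sponsor's SAE form as one of the places. The schedule (Protocol Appendix 1, SAP Table 1) has an AE/SAE check at every visit from week 0 to week 60.

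**The outcome.** Protocol 3.5.2 and SAP 2.2.1 list the "SAE event rate in the 48 weeks of the trial from first dose" as a secondary outcome. The SAP does not define its denominator. SAP Tables 7 and 8 are laid out as counts and percentages over the number of participants.

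**The concern.** In the phrase of 9.3, the thing discontinued is most naturally the trial treatment. Where the protocol means leaving the trial, as in 7.12, it says so. On that reading, 9.3 closes the SAE form for people who are still attending visits, some of them well inside the 48-week outcome window. It is also the section that site staff would consult for SAE forms and 24-hour reporting, so the broader statements elsewhere do not settle what will be done.

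At stake is whether SAE ascertainment depends on how long a participant was dosed. Treatment duration is a post-randomisation variable that tolerability can affect. With table shells that use a fixed number of participants, an SAE left off the form lowers the numerator and leaves the denominator unchanged.

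**Working it through.** The plan gives no figure to reproduce here. The check is date arithmetic on nominal visit days.

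**Inputs**
- Outcome window: 48 weeks from first dose, 48 × 7 = 336 days (Protocol 3.5.2, SAP 2.2.1).
- Dosing: "once every 4 weeks (Week 0, 4, 8, 12, 16, 20, 24, 28, 32, 36, 40, and 44" (Protocol 4).
- SAE-form limit after cessation: 100 days (Protocol 9.3).
- Assumption for the main table: cessation is the date of the last dose.

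**Formula.** For a last dose at week *w*, recording ends on day 7*w* + 100. Uncovered days = max(0, 336 − (7*w* + 100)) = max(0, 236 − 7*w*).

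| Last dose (week) | Recording ends (day) | Uncovered days of 336 | Share |
|---|---|---|---|
| 0 | 100 | 236 | 70.2% |
| 12 | 184 | 152 | 45.2% |
| 24 | 268 | 68 | 20.2% |
| 32 | 324 | 12 | 3.6% |
| 36 | 352 | 0 | 0% |
| 40 | 380 | 0 | 0% |

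The shortfall reaches zero at 7*w* = 236, or week 33.7. The last affected dosing visit is therefore week 32. Stopping after week 36 or 40 costs nothing from the 48-week outcome, only 68 or 40 days before week 60 (day 420).

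**Sensitivity to the date of cessation.** A participant who comes under 7.10 by missing more than one dose reaches that point at the second missed dose, 8 weeks after the last one given. Counting from there, the shortfall is max(0, 336 − (7(*w* + 8) + 100)) = max(0, 180 − 7*w*). That gives 180 days (54%) for a last dose at week 0, 96 (29%) at week 12, 12 (3.6%) at week 24 and none at week 28 or later.

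**Scale across the trial (illustration only).** The documents give a drop-out rate of 10% but no rate of stopping treatment while staying in follow-up. Assume that last doses are spread evenly over the 11 visits from week 0 to week 40, that all stoppers are followed to week 48, and that cessation is the last dose. The mean loss is 1,116 / 11 = 101 days, which is 30% of 336. If 5%, 10%, 20% or 30% of the 80 participants stop early, then 1.5%, 3.0%, 6.0% or 9.1% of the 48-week person-time is uncovered. If all of them stop after the first dose, the figures are 3.5%, 7.0%, 14.0% and 21.1%.

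**The case against.** The strongest reply is that nothing need be lost. Protocol 9.2, the investigator's duty in 9.4 to record and report all SAEs, the check at every visit, and SAP 7 all require capture without a 100-day limit. The SAE-rate outcome is marked as held on the Macro database, whereas 9.3 governs forms sent to the Sponsor. Early discontinuation could also mean leaving the trial without a week-60 visit, which would make the 100 days a fallback for people no longer followed. This stands to the extent that under-counting is conditional on 9.3 being followed. It does not remove the conflict, because SAP 7 names the Sponsor's SAE form and 9.3 closes that form.

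Three stronger readings are tempting, and the documents do not support them.

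- **That late MACE, anaphylaxis and deaths would be missed.** The AESI instruction in 9.3 carries no end date, and 9.6 gives AESIs their own forms and a place on the trial database. Section 9.5 sets no end date for deaths. Section 9.9 has SUSARs reported however late they occur, and under 9.2.1 a treatment-emergent SAE judged related to the drug is a SUSAR. COPD exacerbations are outside the AE definition unless judged related (9.1), and COPD hospitalisations count in the primary outcome, although 9.2.1 partly qualifies this. What remains is mainly non-fatal SAEs that are not AESIs, not COPD events and not judged related.
- **That the anti-ST2 SAE rate is biased downward.** This would need stopping to differ by arm, on which there is no figure, and a fixed denominator, which the SAP does not state. A rate over observed person-time would lose information but need not be too low.
- **That Protocol 9.9 makes the 48-week outcome worse for completers.** It says "ADR will continue to be recorded and reported for up to 3 months after the last dose of IMP has been administered". For a week-44 dose (day 308) that is about day 308 + 91 = 399, beyond day 336. It is a third time limit, for reactions only, and does not shorten the 48-week window for a completer.

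**Conclusion.** The documents contradict each other on how long SAEs are recorded for participants who stop dosing but remain in follow-up. If Protocol 9.3 is applied as written, the 48-week SAE outcome is incomplete for those with a last dose at week 32 or earlier. Per participant, the gap runs from 12 days (3.6%) to 236 days (70%) when counted from the last dose. It is shorter, and ends with a last dose at week 24, when counted from the second missed dose. Both sets of figures assume nominal visit days.

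The effect on the whole trial cannot be fixed from the documents, because they give no rate of stopping treatment while staying in follow-up. A reader might infer that SAEs are under-counted in all early stoppers. That goes too far: other sections require full capture, and stopping after week 36 or 40 costs nothing from the 48-week outcome. This is a should-fix inconsistency affecting a secondary safety outcome; it does not show that the safety comparison is biased.

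**What to change.** 1. **Protocol 9.3:** record SAEs to the final trial visit for everyone still in follow-up, dosed or not. Apply the 100-day limit only to participants who leave the trial. Define early discontinuation to match. A general rule of whichever date is later should be avoided: it would extend recording to week 60 for people whose participation ended at a withdrawal visit under 7.10.
2. **Protocol 9.2, the schedule and SAP 7:** check that they state the same end point as the revised 9.3.
3. **Protocol 7.10 and 8.10:** reconcile them on whether participants delayed more than 4 weeks stay in follow-up or are withdrawn, so that it is clear to whom each recording rule applies.
4. **SAP 7:** define the SAE-rate denominator as each participant's SAE-observed time within the 48 weeks from first dose, and show it beside the counts in Tables 7 and 8.

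The cost is wording in a few protocol sections, a line in the SAP and a small number of additional SAE forms. No visits are added, since the AE/SAE check is already scheduled at every visit to week 60.

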9.4 Responsibilities

Principal Investigator (PI):

- 1. Checking for AEs and ARs when participants attend for treatment / follow-up.
- 2. Using medical judgement in assigning seriousness, causality and whether the event/reaction was anticipated using the Reference Safety Information approved for the trial.

- 3. Using medical judgement in assigning seriousness and causality and providing an opinion on whether the event/reaction was anticipated using the Reference Safety Information approved for the trial.
- 4. Ensuring that all SAEs are recorded and reported to the sponsor within 24 hours of becoming aware of the event and provide further follow-up information as soon as available. Ensuring that SAEs are chased with Sponsor if a record of receipt is not received within 2 working days of initial reporting.
- 5. Ensuring that AEs and ARs are recorded and reported to the sponsor in line with the requirements of the protocol.

Chief Investigator (CI) / delegate or independent clinical reviewer:

- 1. Clinical oversight of the safety of patients participating in the trial, including an ongoing review of the risk / benefit.
- 2. Using medical judgement in assigning the SAEs seriousness, causality and whether the event was anticipated (in line with the Reference Safety Information) where it has not been possible to obtain local medical assessment.
- 3. Using medical judgement in assigning whether and event/reaction was anticipated or expectedness in line with the Reference Safety Information.
- 4. Immediate review of all SUSARs.
- 5. Review of specific SAEs and SARs in accordance with the trial risk assessment and protocol as detailed in the Trial Monitoring Plan.
- 6. Assigning Medical Dictionary for Regulatory Activities (MedDRA) or Body System coding to all SAEs and SARs.
- 7. Preparing the clinical sections and final sign off of the Development Safety Update Report (DSUR).

Sponsor: (NB: where relevant, these can be delegated to CI)

- 1. Central data collection and verification of AEs, ARs, SAEs, SARs and SUSARs according to the trial protocol onto a database.
- 2. Reporting safety information to the CI, delegate or independent clinical reviewer for the ongoing assessment of the risk / benefit according to the Trial Monitoring Plan.
- 3. Reporting safety information to the independent oversight committees identified for the trial (Data Monitoring Committee (DMC) and / or Trial Steering Committee (TSC)) according to the Trial Monitoring Plan.
- 4. Expedited reporting of SUSARs to the Competent Authority (MHRA in UK) and REC within required timelines.
- 5. Notifying Investigators of SUSARs that occur within the trial.
- 6. The unblinding of a participant for the purpose of expedited SUSAR reporting [For double blind trials only].
- 7. Checking for (annually) and notifying PIs of updates to the Reference Safety Information for the trial.
- 8. Preparing standard tables and other relevant information for the DSUR in collaboration with the CI and ensuring timely submission to the MHRA and REC.

Trial Steering Committee (TSC):

In accordance with the Trial Terms of Reference for the TSC, periodically reviewing any safety issues highlighted by the DSMC and acting upon them appropriately.

Data Safety Monitoring Committee (DSMC):

In accordance with the Trial Terms of Reference for the DMC, periodically reviewing overall safety data to determine patterns and trends of events, or to identify safety issues, which would not be apparent on an individual case basis.

9.5 Notification of deaths

All deaths will be reported to the Sponsor in accordance with the SAE reporting timeline described previously and within 24hours of the investigator becoming aware of it.

